8.4.2 Documentation and Reporting Obligations: INVESTIGATOR

Serious Adverse Events have to be documented on the SAE-forms and the investigator must report them to the sponsor immediately. If more information about the SAE becomes available later, it must also be reported to the sponsor immediately.

SAE reporting will be performed from first injection of the study drug (Visit 1) up to 4 weeks after the last trial-related intervention, which is (at latest) Visit 24.

In the event of a patient’s death, the investigator/deputy or the authorised medical staff provides the leading ethics committee(s), all involved ethics committees in multi-centred trials, the responsible federal authorities and the sponsor with all further information needed to fulfil their tasks **upon request**.

In all the reports, personal data are to be pseudonymized by using the patient’s identification code. It must be possible to relate the initial and all follow-up reports to each other by means of the patient identification number.

1 In general, hospitalisation means that the patient stays (usually at least an overnight stay) at the hospital or emergency ward for observation and/or treatment. Complications that occur during the stay are AEs. If a complication prolongs hospitalisation or fulfills any other serious criteria, the event is serious.

Hospitalisation for elective treatment of a pre-existing condition that did not worsen from baseline is not considered an AE.

The investigator, the deputy or the authorised medical staff must report every Serious Adverse Event as soon as getting knowledge of it to the following address:

ZKS Leipzig/Pharmacovigilance
 Universität Leipzig
 Zentrum für Klinische Studien Leipzig
 [name]
 [contact]
E-mail: [contact]

[contact]

8.4.3 Documentation and Reporting Obligations: SPONSOR

After the ZKS Leipzig receives the SAE, it is immediately passed on to the coordinating investigator/responsible person for medical assessment.

The coordinating investigator/responsible person forms a second medical opinion of the SAE with respect to causal relationships and the decision as to whether or not it was expected, as described in chapter 18.1.3 and 18.1.4 and forwards the second opinion to the ZKS Leipzig within two days of its arrival.

In the ZKS Leipzig the SAE data are entered into the SAE database immediately and the MedDRA coding takes place simultaneously.

Then forwarding as per law and as described in Chapter 8.5 only for Suspected Unexpected Serious Adverse Drug Reactions (SUSARs) takes place.

Details of the sponsor's documentation and reporting obligations will be specified in a special, trial-specific pharmacovigilance plan, which will be written and finalised alongside with this protocol, if possible.

8.4.4 Annual Safety Report

According to German Medicinal Products Act the sponsor writes a safety report annually (Annual Safety Report, ASR²) and sends this report to the leading ethics committee(s) and the federal authority/ies.

The key date is the date of the first authorization of the clinical trial by a federal authority. All data obtained up to this date (each year) will be included in the ASR. Beginning with the key date, there is a time-limit of 60 days for the preparation and submission of the ASR.

The ASR will be prepared by the ZKS Leipzig (project manager, responsible biometrician and PV data manager) acc. to the national requirements deadlines regarding the ASR based on the German Medicinal Products Act. The final report will be released in co-operation with the sponsor's representative.

2 See "Detailed guidance on the collection, verification and presentation of adverse reaction reports arising from clinical trials on medicinal products for human use").

8.5 Suspected Unexpected Serious Adverse Reactions (SUSAR)

8.5.1 Documentation und Reporting Obligations

Information for SPONSOR

The sponsor submits all information available about a SUSAR immediately to the leading ethics committee, the responsible federal authorities, and to all participating primary investigators, at the latest within 15 calendar days after the event becomes known.

For every SUSAR that results in death or a life-threatening condition, the leading ethics committee, the federal authority, and all participating investigators must be informed by the sponsor within 7 calendar days after the event becomes known. Additional information has to be given within 8 further calendar days.

Details of the sponsor's documentation and reporting obligations will be specified in a trial-specific pharmacovigilance plan, which will be written and finalised alongside with this protocol.

Information for INVESTIGATOR

The investigator passes down all relevant information concerning the SUSAR to all participating trial staff at his trial centre. This has to be confirmed by the investigator by signing an acknowledgement document.

8.6 Dealing with Pregnancy

Every pregnancy that occurs while taking part in the trial must be reported to the ZKS Leipzig by the investigator/deputy or the authorised medical staff within 24 hours of having learned of it by informal communication:

ZKS Leipzig / Pharmacovigilance
Universität Leipzig
Zentrum für Klinische Studien Leipzig
[name]
Telefon: [name]
[contact]
E-mail: [contact]

The ZKS Leipzig will then supply the essential forms for documentation to the investigator/deputy investigator without unduly delay. Pregnancies that occur in female trial subjects have to be reported by using the form: "Report on the arising of a pregnancy during exposition to a trial medication". Severe side effects and complications during a pregnancy as well as congenital birth defects are Serious Adverse Events by definition and therefore also have to be reported on the Serious Adverse Event form according to the reporting procedures described above.

The outcome of a pregnancy has to be reported on the form "Report on the outcome of a pregnancy during/after exposition to a trial medication". This form will document the outcome of the pregnancy, including a spontaneous or voluntary abortion, details of the birth process, the presence or absence of congenital malformations and birth defects, maternal or foetal complications and the potential relationship to the trial drug.

Collecting data concerning the outcome of a pregnancy is only permitted if the trial subject puts down her permission in writing beforehand. The collection of data on the child's health requires the prior information and consent of the guardian/parents (usually both).

9 BIOMETRY

9.1 Biometrical Aspects of the Trial Design

This is a randomized parallel-group trial with two arms:

- Experimental group, in which patients will receive injections of Ranibizumab and additional targeted laser photocoagulation in areas of non-perfusion at pre-specified time points if indicated.
- Control group, in which patients will receive the standard intravitreal injections of Ranibizumab as per current treatment guidelines only.

All patients will be followed for 29 months after randomisation to identify a treatment success, in case the first time without need for re-injection is the last visit with planned re-injection (EoT, at month 23), and to evaluate the long-term development of BCVA and CST.

9.1.1 Measures to Prevent Bias

Remote computerised randomisation 1:1 via internet will be provided. Randomisation will be stratified by baseline BCVA (≤ 55 letters vs $55 >$ letters) as sole patient-centred criterion. The stratification according to baseline BCVA reflects the differences in the natural prognosis of CRVO patients treated with Ranibizumab [27].

Handling bias should be negligible because maintenance injections will follow pre-defined re-treatment criteria guided by morphologic OCT criteria.

To achieve the highest possible standardization of the laser photocoagulation, the evaluation of FA images and indication of the peripheral retinal areas for laser treatment will be performed centrally by the CoRaLa II Central Reading Center (see chapters 3.2). A consented plan containing the localisations will be transferred to the patient's site, where the laser treatment is performed.

ITT analysis within the full analysis set of patients (FAS) acc. to ICH E9 guideline [20] will ensure an unbiased analysis. Regular supervision of study documentation and established query management will ensure data quality and completeness [21].

9.2 End Points

9.2.1 Primary End Point

Primary efficacy endpoint is the time to treatment success, defined as time from randomisation until the date of last criteria-based intravitreal injection in case that thereafter a treatment-free period for (at least) 6 months was observed.

Objective criteria for further treatment indication (according to details in section 6.3) have to be fulfilled for decisions regarding further re-treatment.

Drop-outs/deaths without earlier success will be censored at the end of their observation time and all other patients without documented success at month 24 or 29 after randomisation (in case of no treatment indication at the last regular visit to state or deny a late success).

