After stating success of treatment (treatment-free interval \geq 6 months) all patients will be seen at all "mandatory visits" later on in the course of trial. These visits are planned at month 16, 20, 24 and 29. For all patients without earlier "success" last possible Ranibizumab injection within the trial is at month 23 (End of treatment; EoT). Patients, who required further treatment will be treated after month 23 out of trial. All patients will be asked to come for the observational visit at month 29 to assess visual acuity, retinal thickness, the (latest) success possible, and to document the potential late relapses of the edema, which required the treatment out of the trial.

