6.3 Description of the Treatment Procedures

Intravitreal injections of Ranibizumab will be applied in all patients according to treatment guidelines. The experimental group will receive an additional targeted laser photocoagulation of the peripheral areas of capillary non-perfusion (up to 4 laser treatments within 1st year of the study). No further additional treatments of the study eye will be given in any of the arms of the trial.

Intervention scheme of CoRaLa II Trial

* complementary endpoints in all patients at month 24.

** secondary endpoints in patients with success at that visit when success is stated; in patients without treatment success prior to visit 24, secondary endpoints will be assessed at month 29; if a patient needs treatment after success, this treatment is no longer a study treatment and therefore no further AE/SAE documentation is needed.

Based on the results of optical coherence tomography (OCT) the **diagnosis of ME** will be established and Ranibizumab injections will be indicated.

Pre-defined re-treatment criteria will be applied according to treatment guidelines in order to identify a further need of re-injections at the monthly visits.

Re-treatment with Ranibizumab is needed if the following criteria are met:

- persisting ME or
- recurrence of ME

defined as presence of intra-/sub-retinal fluid and /or central subfield thickness (**CST**) of **≥250 µm** assessed by OCT

Re-treatment criteria for laser photocoagulation: new areas of capillary non-perfusion detected with fundus photography and FA at 3 and 9 months after randomisation. Experienced graders of the CoRaLa II Central Reading Center will evaluate all fundus and FA images taken with the Zeiss 700 device and define the non-perfused retinal areas for laser photocoagulation. Laser photocoagulation will be performed at Month 2 and if needed at Months 4, 6 and 10.

Parameters needed for end-point evaluations:

- Only if no ME can be identified by OCT over 6 months of follow-up **treatment success** is stated and the time until this visit will be used in confirmatory analysis.

- **The number of Ranibizumab injections** depends on the valid assessment of presence/ or absence of ME in all monthly visits and will be counted until defined success (if applicable) and at the end of study.

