9.4 Sample Size Discussion

Long-term review of CoRaLa I [10] patients (as reported in 1.2) showed that a proportion of $p_{R\text{-only}}=0.58$ had to be treated longer than 2 years, while for all but one patient ($p_{RL}=0.1$) the combined therapy could be terminated after median [quartiles] of 10 [3;11] months but total observation times of 18 [16; 20] months.

Assuming 2 years to treatment success, rates of 50% with R-only and (conservative) 20% with RL, setting a two-sided significance level α at 5%, and requiring 90% power we need a total of $N=92$ cases with a log rank test.

With regard to the number of injections applied within two years (without the three initial monthly injections), we observed 5.6 (4.9) injections (mean (SD)) in the R-only, but 2.8 (2.7) in the RL-group. Based on these means (SD), we need $n=46$ patients per group with an α level of 5% (2-sided) and for a power of 90%.

Non-compliance and dropout rates are expected to be rather low with regard to the massive impact of impaired visual acuity on activities of daily and social living. Regarding the CoRaLa I patients one participant (of 22) was lost (after 15 months) and 2 per arm died after long-term observation of more than 4 years. Although (extended) oversampling is not needed with regard to the confirmatory analysis within the FAS and a time-to-event primary endpoint, a major interest of the trial focuses on mid-/long-term differences between the treatments, too. Therefore, we amply plan with 20% dropouts and intend to include at least 110 patients to learn as much as possible on the effect of the additional laser treatment on the further need of regular Ranibizumab injections in long-term and ensure sufficiently precise estimations after two year of observation.

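### Section 9.2.1 dates success at the last injection but censors drop-outs and deaths at end of observation, so up to 6 months in which no success can be recorded count as event-free; section 6.3 uses a different event date

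*Protocol*

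**What the plan says.** The endpoint definition in section 9.2.1, repeated in the synopsis, counts time from randomisation "until the date of last criteria-based intravitreal injection in case that thereafter a treatment-free period for (at least) 6 months was observed".

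Section 9.2.1 then fixes the censoring. For patients who leave: "Drop-outs/deaths without earlier success will be censored at the end of their observation time". The rest are censored as "all other patients without documented success at month 24 or 29 after randomisation".

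Section 6.3, which lists the parameters needed for endpoint evaluation, gives a different date. Once 6 months without macular edema have been seen, success "is stated and the time until this visit will be used in confirmatory analysis". That visit falls about 6 months after the last injection.

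Two further facts bound the problem. Section 1.2.1 says that for patients without earlier success the "last possible Ranibizumab injection within the trial is at month 23", and all patients are asked to attend at month 29. On drop-out, section 9.4 expects little (one of 22 patients lost in the earlier study) but adds: "Therefore, we amply plan with 20% dropouts".

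**The concern.** Under 9.2.1 a success at month T enters the data only if the patient is still observed at T + 6. A patient who leaves at month D can therefore have a recorded event only if T is at most D − 6. The censoring rule still keeps that patient in the risk set as not yet successful until D. Between D − 6 and D the patient counts in the denominator but cannot supply an event.

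Example: last injection at month 10, dry at months 11 to 14, lost at month 15. The treatment may well have ended successfully at month 10. It cannot be confirmed, and the patient is counted as without success for five further months.

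This pulls the estimated success rate down in any arm that loses patients. If the arms lose patients at different rates, the pull is unequal and carries over into the confirmatory Cox hazard ratio.

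**Working it through.** **The plan's own figure.** Section 9.4 gives 2-year rates of 50% (R-only) and 20% (RL), two-sided 5%, 90% power and N = 92. Read as proportions still without success, with exponential times, the success hazard ratio is ln(0.2)/ln(0.5) = 2.32. Schoenfeld's formula gives 4 × (1.960 + 1.282)² / (ln 2.32)² = 59.2 events. The mean success probability is (0.5 + 0.8)/2 = 0.65, and 59.2/0.65 = 91.1, or 46 per arm and 92 in total. The figure reproduces, so the same rates are used below.

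**Who is affected.** The last event date is month 23, and 23 + 6 = 29, so anyone observed to month 29 is fully ascertained. Censoring such a patient at month 24 or 29 does not alter a Cox model whose events all lie at or before month 23. Only patients lost before month 29 matter.

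**One clock.** There are two consistent pairings: event at T with censoring at D − 6, or event at T + 6 with censoring at D. The second is the first moved by a constant 6 months. The order of times, and so the risk sets and the Cox partial likelihood, are the same. Section 9.2.1 pairs T with D.

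**Hazard ratio.** Simulation of 110 patients, 1:1, 3,000 runs per row. Success times are exponential with the 9.4 rates. Drop-out is exponential, scaled to the stated share by month 29 and independent of success. An event is recorded if T ≤ 23 and T + 6 falls within observation. The Cox model has treatment as its only covariate. A hazard ratio (HR) above 1 favours RL.

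| Drop-out R-only / RL | HR, 9.2.1 rule | HR, one clock | Power, 9.2.1 rule | Power, one clock |
|---|---|---|---|---|
| 4.5% / 4.5% (1/22) | 2.34 | 2.34 | 93% | 93% |
| 20% / 20% | 2.32 | 2.33 | 90% | 90% |
| 10% / 30% | 2.21 | 2.36 | 86% | 91% |
| 30% / 10% | 2.48 | 2.35 | 93% | 90% |
| 10% / 30%, no true effect | 0.94 | 1.00 | 5.0% (type I error) | 4.3% (type I error) |

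Both one-clock pairings gave the same hazard ratio in every row. A larger run of the null case (4,000 patients, 150 runs) gave 0.947 against 1.001.

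**Patients involved.** At 20% per arm about 22 of 110 drop out, about 16 of them without documented success. About 3 of these (1.1 R-only, 1.8 RL) had already had their last injection. They carry on average about 3 months of false event-free time, and always less than 6.

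**Kaplan-Meier curves.** Under the 9.4 rates true success at month 23 is 1 − 0.5^(23/24) = 48.5% and 1 − 0.2^(23/24) = 78.6%. A simulation with 40,000 patients per arm, monthly injections from month 3, and 20% drop-out per arm spread evenly over months 3 to 29 gave 46.6% and 76.7% under the 9.2.1 rule. Censoring at D − 6 gave 48.5% and 78.8%. The curves read about 2 points low.

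**The case against.** The strongest reply is section 6.3. If success is dated at the confirming visit, censoring at end of observation is right and nothing is wrong with the rule itself. Moving only the censoring date back would then create the mismatch it was meant to cure. This stands. It means the event date must be settled first. It does not clear 9.2.1, because that section and the synopsis both date success at the injection.

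The second reply is size. The hazard ratio moves only if drop-out differs by arm, and the protocol gives no figures by arm. It expects low loss, and section 6.5.1 offers the month-29 visit to patients who stop therapy early unless they withdraw consent, so stopping treatment is not the same as leaving observation. Under 10%/30% the shift on the log scale is ln(2.36/2.21) = 0.066, while the standard error with 60 events is about 2/√60 = 0.26. This too stands, and it limits the importance of the point. Unequal loss remains possible, since only one arm has laser sessions.

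A reader might infer more than the documents support:

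- *That the confirmatory test is invalid.* With no effect and 10%/30% drop-out, the simulated type I error at n = 110 was 5.0%.
- *That the planned 20% drop-out by itself biases the hazard ratio.* With equal loss it is 2.32 against 2.33.
- *That the rule favours the laser arm.* The direction depends on which arm loses more patients. Greater loss in RL works against RL.
- *That 6 months are unknown for every drop-out.* A patient injected at the last visit has almost no unknown time, so 6 months is an upper bound.

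**Conclusion.** The point holds in a limited form. As 9.2.1 is written, event and censoring times run on different clocks, and 9.2.1 and 6.3 disagree on the date of the primary event. The consequence is confined to patients truly lost before month 29.

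Kaplan-Meier success reads about 2 points low per arm at 20% drop-out. The hazard ratio is practically unchanged with equal drop-out and shifts by about 0.15 under an assumed 10%/30% split (2.21 against 2.36; about 0.95 instead of 1.00 under the null). At the loss seen in the earlier study the effect is negligible.

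These sizes rest on exponential success times, drop-out independent of outcome, and drop-out splits that are assumptions and not protocol figures. The mismatch itself follows from the definitions and needs none of them. Minor to moderate importance.

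**What to change.** First decide which event date governs and make 9.2.1, 6.3 and the synopsis agree. Then use one of two consistent pairs.

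(a) Keep success at the last injection. In 9.2.1, censor drop-outs and deaths without confirmed success 6 months before their last assessment of injection need, but not before randomisation, and delete the conflicting date in 6.3.

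(b) Date success at the confirming visit, as 6.3 does, and keep censoring at end of observation. Events then run to month 29, so patients observed to the end without success must stay at risk until month 29 and not leave at month 24. The calculation above was done that way. Reported times to success become about 6 months longer.

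Both give the same hazard ratio. Censoring drop-outs at their last injection is not a substitute: with 10%/30% drop-out and no effect it still gave 0.955. The present rule can stay as a sensitivity analysis.

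The cost is a sentence or two in the protocol and the matching text in the SAP, with no new data, and it should be settled before database closure. Under (a), patients lost before month 6 contribute no time. If drop-out is spread evenly over months 3 to 29, that is (6 − 3)/26, or about 12% of drop-outs. Neither option removes bias when drop-out depends on outcome: with a fivefold drop-out rate after the last injection, the hazard ratio was 2.29 under the present rule, 2.39 on one clock and 2.34 with complete data.

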1.3 Risk-Benefit Considerations

The treatment with Ranibizumab in the control group, as well as in the experimental *group* are standard therapies, described in German treatment strategies [5]. Standard care will follow defined re-treatment criteria for Ranibizumab injections according to guidelines [1].

Laser photocoagulation of the retina is well established treatment technique for ischemic retinal disorders as diabetic retinopathy or retinal vein occlusions. Since decades, panretinal (scatter) laser photocoagulation is used for treatment of the neovascular complications as e.g. vitreous bleeding, neovascular glaucoma or tractive retinal detachment. However, the Central Vein Occlusion Study Group did not find any significant benefit of profilactic panretinal (non-selective) scatter laser photocoagulation in patients with ischemic CRVO [24]. This study focused on ischemic cases only, which have a poor natural prognosis and did not evaluate the visual acuity. Therefore, the implication of these results for current treatment strategy is strongly limited.

Since no established evidence exists on potential benefits of laser therapy as add-on-treatment to usual care (Ranibizumab injections) randomized treatment allocation appears justified.

Intravitreal (IVT) injection of Ranibizumab used in this study will be given according to the label and follow the German treatment strategies [5]. The most serious possible risks of IVT are endophthalmitis and retinal detachment.

The possible risks and side events after retinal laser photocoagulation are the local pain, and temporary increased intraocular pressure. Late side effect of this treatment may be defects in the visual field. In the CoRaLa II trial, the laser photocoagulation will be performed targeted in non-perfused retinal areas only and therefore it is not expected that significant defects of visual field will occur. However, the visual field will be evaluated at the beginning of maintenance phase at month 4 and at end of study to confirm this expectation.

It is expected that the total amount of required IVT can be reduced in the experimental group (combined treatment Ranibizumab and selective laser) compared with controls (Ranibizumab only).

Patients who develop neovascularization of the retina or in the anterior segment (rubeosis iridis) will be withdrawn from the study and receive a rescue panretinal laser photocoagulation (PRP) as a full scatter.

2 Objectives

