5.3.4 Alternative Medication

Patients may not receive any treatment (approved or investigational) for their CRVO in the study eye other than the study treatment with Ranibizumab. Patients without response to Ranibizumab will be switched to an alternative intravitreal drug (Aflibercept or Dexamethasone implant), which will be given out of the study (see chapter 6.5).

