6.5.2 Rescue Treatment

Patients with progress of neovascular complication (Increase of NVE's or NVD's, neovascular glaucoma) will receive rescue treatment with pan-retinal photocoagulation (PRP) outside the study intervention.

Patients with persisting macular edema without response to Ranibizumab will be treated with intravitreal Aflibercept (Eylea) or dexamethasone implant (Ozurdex) out of the study.

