9.5.2 Planned Methods for Analysis

Analysis of the *primary endpoint* (within the FAS, [31]) will follow the intent-to treat principle and will be based on COX regression with the stratification factor baseline BCVA (≤ 55 letters vs > 55 letters) as fixed covariate for confirmatory analysis.

Further models will include potentially prognostic factors and compliance for sensitivity reasons. The assumption of proportional hazard may be justified although no similar data are available by now. It will be checked and otherwise adequately dealt with. Kaplan-Meier curves provide time without treatment success per arm.

The *number of Ranibizumab injections* required after the initial three injections will be analysed by an ANCOVA *model* including treatment as factor and baseline BCVA as covariate (also used for stratification); for sensitivity reasons, further models may include the same prognostic factors of potential relevance as selected for analyses of the primary endpoint.

To adequately analyse the long-term *courses of BCVA and CST* at the end of study we require that patients with early treatment success have further mandatory visits beyond success since - based on CoRaLa I data - we expect rather different event times with regard to the chosen primary endpoint. Given the 6 monthly visits to determine "success", we assume that this will lead to only few additional visits per patient

In each patient, BCVA and CST will be analysed at 6 time points: at baseline visit, and after 12, 16, 20, 24 and 29 months. Analyses of both secondary endpoints are identically structured: mean changes from baseline mean will be analysed using a repeated measurement linear mixed model without intercept containing the fixed, categorical effects of

- visit (as named),
- treatment (RL vs R-only),
- treatment by visit interaction,
- low BCVA pre-treatment value (yes / no) as well as
- a patient-specific, visit random effect.

An unstructured (co-)variance structure will be used to model the residual within-patient errors. If this analysis fails (does not converge), a compound symmetry structure corresponding to a constant correlation will be used. The analysis will be based on restricted maximum likelihood

(REML). The contrast of interest is the treatment by visit interaction at 29 months. Respective inference will be based on Wald type confidence intervals and respective p-values.

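### Section 9.2.1 censors drop-outs without defining them, so patients taken off trial therapy for neovascularisation or non-response may be censored at exit, which is informative censoring in the primary Cox model

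*Protocol*

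**What the plan says.** The primary endpoint (9.2.1) is the "time from randomisation until the date of last criteria-based intravitreal injection in case that thereafter a treatment-free period for (at least) 6 months was observed". The censoring rule follows in the same section: "Drop-outs/deaths without earlier success will be censored at the end of their observation time". The sentence goes on to censor the remaining patients with no recorded success at month 24 or month 29. So there are two classes of patient without success: drop-outs and deaths, censored when their own observation ends, and everyone else, censored at month 24 or 29. Neither class is defined further, and no rule is given for a change of drug or for rescue laser.

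Other sections describe patients who could fall into either class:

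- Section 1.3: "Patients who develop neovascularization of the retina or in the anterior segment (rubeosis iridis) will be withdrawn from the study". They then receive panretinal laser, which 6.5.2 describes this way: such patients "will receive rescue treatment with pan-retinal photocoagulation (PRP) outside the study intervention".
- Section 5.3.4: "Patients without response to Ranibizumab will be switched to an alternative intravitreal drug", given off study. Section 6.5.2 agrees: "Patients with persisting macular edema without response to Ranibizumab will be treated with intravitreal Aflibercept" or a dexamethasone implant, off study.
- Section 6.5.1 lists both situations as possible reasons for ending trial therapy early. It offers all these patients, apart from those who withdraw consent, the month 29 visit, on the ground that the primary endpoint is recorded there.
- Section 9.1 plans 29 months of follow-up for every patient.

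The primary analysis (9.5.2) "will follow the intent-to treat principle and will be based on COX regression with the stratification factor baseline BCVA". The sensitivity models named there add prognostic factors and compliance; none addresses the censoring rule.

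**The concern.** Cox regression treats a censored patient as having the same later chance of success as the patients of the same arm and BCVA stratum who are still at risk. That is reasonable for a missed appointment. It is not reasonable for an eye that leaves because its edema does not respond, since section 6.3 requires six months without edema on OCT before success can be stated. The reason for leaving is then failure on the outcome itself. Progression to neovascularisation is a less direct link, but it too is an exit caused by the course of the disease.

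If such exits are coded as drop-outs, the success curve of the arm with more of them is raised and the hazard ratio shifts. Unequal exit between arms is conceivable. Laser is given in one arm only, blinding is described only for the BCVA assessor (3.2.1, 6.3), non-response has no stated threshold, and 6.5.1 leaves room for investigator discretion. At stake are the size of the treatment effect and, if exit is unequal, the error rate of the confirmatory test.

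**Working it through.** **Which class does each patient fall into?**

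- Rescue laser: section 1.3 ends study participation, so observation ends at exit and 9.2.1 censors there. Sections 6.5.1 and 9.1 say the opposite. The text conflicts, and censoring at exit is the direct reading of 1.3.
- Non-response: sections 5.3.4 and 6.5.2 place the new treatment outside the study but do not say that observation stops. With 6.5.1 and 9.1 the patient can be followed to month 29 and censored at month 24/29. With drop-out undefined and the visit only offered, censoring at the switch is also possible.

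**The plan's own figure.** Inputs from section 9.4: 50% (R-only) and 20% (RL) without success at 2 years, two-sided 5%, 90% power, N = 92.

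- Success hazard ratio = ln 0.20 / ln 0.50 = 2.32.
- Events (Schoenfeld) = 4 × (1.960 + 1.282)² / (ln 2.32)² = 59.2.
- Mean event probability = (0.50 + 0.80) / 2 = 0.65, so N = 59.2 / 0.65 = 91.1. Rounding events up to 60 first gives 92.3.

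The stated 92 is reproduced. The sample size is not in dispute; it fixes the scenario.

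**Effect of the censoring rule.** Simulation with 55 patients per arm, exponential time to success, 4000 runs per row, unadjusted Cox hazard ratio (RL vs R-only) and log-rank test at two-sided 5%. Assumptions not in the protocol: a share q of the eyes without success by month 23 is switched or rescued, at a time uniform over months 4 to 12. These eyes are either kept at risk as non-successes to month 24 or censored at exit.

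| True 24-month success, R-only / RL | q, R-only / RL | Share of all patients leaving | Kept: HR, rejection | Censored at exit: HR, rejection |
|---|---|---|---|---|
| 50% / 80% | 0 / 0 | 0 / 0 | 2.35, 94.5% | 2.35, 94.5% |
| 50% / 80% | 20% / 20% | 10.2% / 4.2% | 2.33, 93.5% | 2.27, 91.9% |
| 50% / 80% | 40% / 40% | 20.6% / 8.5% | 2.34, 93.8% | 2.22, 90.5% |
| 50% / 80% | 60% / 60% | 31.0% / 12.8% | 2.36, 94.0% | 2.14, 87.6% |
| 50% / 80% | 40% / 0 | 20.6% / 0 | 2.33, 93.5% | 1.91, 75.8% |
| 50% / 80% | 0 / 40% | 0 / 8.6% | 2.34, 93.2% | 2.71, 98.4% |
| 50% / 50% | 20% / 20% | 10.3% / 10.3% | 1.01, 5.5% | 1.01, 5.3% |
| 50% / 50% | 0 / 20% | 0 / 10.4% | 1.00, 5.3% | 1.11, 6.9% |
| 50% / 50% | 0 / 40% | 0 / 20.7% | 1.00, 5.5% | 1.25, 13.8% |
| 50% / 50% | 40% / 0 | 20.7% / 0 | 0.99, 5.3% | 0.79, 13.4% |

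Monte Carlo standard error of a 5% rejection rate is √(0.05 × 0.95 / 4000) = 0.34 percentage points, so 6.9% and above is not noise.

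Three things follow. With equal q and a true benefit, R-only loses more failures and the estimate moves towards no effect. With equal q and no difference, the error rate holds. Distortion in either direction, and an inflated error rate, require unequal exit. Keeping these eyes in the risk set restores a hazard ratio of about 2.3 to 2.4 with 93 to 95% power, or about 1.0 with roughly 5% error.

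**The case against.** The strongest reply is that the second half of the 9.2.1 sentence already does what is needed: a patient still observed without success is censored at month 24 or 29, which is the same as staying at risk as a non-success. Sections 6.5.1 and 9.1 support this for anyone who stops therapy, and the off-study wording in 5.3.4 and 6.5.2 describes the treatment, not the end of observation. For non-responders this is a fair reading, perhaps the better one. A reader might infer that the protocol orders their censoring at the switch; it does not. What remains is that drop-out is undefined, the month 29 visit is optional, and section 1.3 does withdraw the neovascularisation patients.

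A reader might also infer that a switched eye could be recorded as a success because it receives no more ranibizumab. The text gives this little support: 9.2.1 asks for a treatment-free period and names no drug, and 6.3 requires the absence of edema on OCT. But an eye may be dry because of the off-study drug, so an explicit sentence is worth having.

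Nor is rescue laser a known non-success. The endpoint concerns injections for macular edema, and an eye treated for neovascularisation may still go six months without them. Scoring it as failure is a choice of estimand.

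Finally, the rates are assumed. The only loss reported in 9.4 is 1 of 22 patients, and no switching rate is given. Scenarios with a large bias in favour of laser need heavy exit: 15% of all RL patients leaving would be 15 / 20 = 75% of that arm's expected non-successes. The documents do not support presenting such a case as likely.

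Details of a drug switch could be left to the SAP. The protocol, however, fixes the censoring rule itself and contradicts itself on who remains in the study.

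**Conclusion.** The point holds as a conflict in the text with a possible bias in the primary analysis, not as a proven bias. Following section 1.3 with 9.2.1 censors rescue-laser patients at exit; non-responders may be handled the same way. Such censoring is informative, and adjustment for the baseline BCVA stratum does not remove it.

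The size is conditional on assumed rates. It is small if switching is low and equal (hazard ratio about 2.35 to 2.27, power 92%). If 40% of non-successes leave in one arm only, the hazard ratio lies between 1.91 and 2.71 and power between 76% and 98%. With no true difference and 0% versus 20 to 40% of non-successes leaving, two-sided error is about 7 to 14%. These figures also assume that every eye that leaves would not have succeeded by month 23; if some would have, the distortion is smaller. A reader might infer that the rule favours the laser arm; the direction is open, and under equal switching with a true benefit it works against that arm.

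**What to change.** In section 9.2.1 state that:

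1. Ending trial therapy is not dropping out.
2. A patient switched to another intravitreal drug before success stays in the risk set as a non-success to month 24/29.
3. Any intravitreal drug for macular edema in the study eye, on or off study, breaks the six-month treatment-free period.
4. Patients given rescue photocoagulation stay in follow-up and in the risk set to month 24/29, with a sensitivity analysis that counts rescue as non-success.
5. Censoring at last observation applies only to loss to follow-up, consent withdrawal and death.

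Reconcile the withdrawal statement in section 1.3 with the follow-up to month 29 in sections 6.5.1 and 9.1. No change to clinical management is proposed; this concerns observation and coding only.

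The cost is a few sentences. The month 29 visit is already offered to these patients, though the dates of off-study intravitreal treatment must be available for them. The price in interpretation is that item 2 is a composite strategy, so the hazard ratio describes success without a change of drug rather than any eventual end of injections.
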